6.5 Drug Concentration Measurements and Pharmacokinetic Parameters

Not Applicable.

6.5.1 Handling of Pharmacokinetic Parameter Outliers

Not Applicable.

6.6 Safety Assessments

The safety endpoints will be listed and/or summarized by dose cohort.

- Number of Adverse events (AE),
- Number of Grade 3/4 AEs.
- Death

Document Date: 12MAY2023

Number of Serious adverse events (SAE) evaluated and graded using NCI-CTCAE Version 5.0.

6.6.1 Duration of Treatment Exposure and Compliance to Study Treatment

Treatment compliance and the treatment exposure will be summarized descriptively (n, mean, median, standard deviation, minimum and maximum values) and will also be listed.

> Page 10 of 106 ST-AD-032 version 01

6.6.2 Clinical Laboratory Evaluations

Change from baseline for each visit will be defined as the visit value minus the baseline visit value.

6.6.3 Other Observations Related to Safety

Vital Signs

Absolute value of vital signs parameters will include summaries for systolic and diastolic blood pressure, temperature, pulse, respiratory rate and weight.

Vitals will be done prior to the administration of study treatments, at the time points specified in schedule of events.

Electrocardiogram (ECG)

Absolute value of ECG parameters will include summaries for heart rate, PR, QRS, QT, and QTcF intervals.

Physical Examination

The investigator/qualified designee will perform a complete physical exam during the screening period and as defined in Schedule of Events. Physical examination will include systemic examination (General Appearance, HEENT, neck, cardiovascular, lungs, abdomen, lymph nodes, genitourinary (as applicable), extremities, neurological, skin, and musculoskeletal). Physical examination also includes measurement of accessible nodes and the size of the spleen and liver.

- **ECOG Performance Status**
- Medical and Surgical History
- **Prior and Concomitant Medications**

6.7 Pharmacodynamics Parameters

Not Applicable.

7. STATISTICAL METHODS

7.1 General Methodology

All statistical analyses will be performed using SAS 9.4 or higher.

Continuous data will be summarized using descriptive statistics (number of patients (n), mean, standard deviation (SD), median, minimum, and maximum). Summary statistics for continuous measures will be provided for baseline, the actual measurements at each visit, and where appropriate, the change from baseline measurements to each visit. Discrete data will be summarized using frequency counts and percentages and where appropriate, the 95% Confidence Intervals (CIs) will be presented.

When count data are presented, the percentage will be suppressed when the count is zero in order to draw attention to the non-zero counts. A row denoted "Missing" will be included in count tabulations where

CONFIDENTIAL Page 11 of 106 Document Date: 12MAY2023 ST-AD-032 version 01

necessary to account for dropouts and missing patients. Unless otherwise specified, the denominator for percentages will be the number of patients with a non-missing assessment in a given treatment group within the analysis population of interest.

All the patient data will be summarized by treatment group and overall.

The following sub-group analysis will be performed only for demographics, baseline characteristics and efficacy tables:

1. de novo metastasis, recurrent (locoregional/distal) metastasis and Overall

Patient listings of all data from the case report forms (CRFs) as well as any derived variables will be presented.

7.2 Adjustments for Covariates

Not applicable to this study

7.3 Handling of Dropouts or Missing Data

Missing results/events will not be imputed. Imputations will be done for missing dates as follows.

Missing Dates for Adverse Events and Concomitant Medications

Adverse events and concomitant medications with completely or partially missing assessment dates will have imputation performed as explained below for the purposes of calculation of durations or relativity to study medication.

For the end of a concomitant medication or adverse event:

If only Day of end date is missing:

The last date of the month and year reported or the date of the final contact with the patient, whichever is earlier, will be used as the end date.

• If Day and Month of end date are missing:

The last date of year i.e. December 31 of the year reported or the date of the last study contact with the patient, whichever is earlier, will be used as the end date.

If Year of end date or complete end date is missing:

If the year of end of medication/event is missing or end date is completely missing, then no end date will be imputed.

For the start of a concomitant medication or adverse event:

• If only Day of start date is missing:

o If the start year and month of medication/event are the same as that for the first dose date, then following approach will be used:

CONFIDENTIAL Page 12 of 106

Document Date: 12MAY2023. ST-AD-032 version 01

- If the end date of medication/event is NOT before the first dose date or end date of medication/event is completely missing, then impute the start day as the day of first dose date
- Otherwise, impute the start day as 1.
- If the start year and month of medication/event are NOT same as that for the first dose date. then
 - Impute the start day as 1.

If Day and Month of start date are missing:

- If start year of medication/event is same as first dose year, then following approach will be used:
 - For medication, impute the start Month as January and the Day as 1 İ.
 - ii. For adverse event.
 - If the end date of event is NOT before the first dose date or end date of event is completely missing, then impute the start Month and Day as the Month and Day of first dose date;
 - Otherwise, impute the start Month as January and the Day as 1.
- If start year of medication/event is NOT same as first dose year, then
 - Impute start Month as January and the Day as 1.

If Year of start date or complete start date is missing:

If the year of start of medication/event is missing or start date is completely missing, then no start date will be imputed.

Missing Dates for Efficacy Endpoints

For time-to-event endpoint if the date is completely missing, no imputation will be performed. However, the incomplete/partial dates will be handled following the general conventions as detailed for adverse events and concomitant medications.

Missing dates for Primary Diagnosis/Prior therapy

Partial Primary diagnosis and prior therapy dates will have imputation performed as explained below for the purposes of calculation of relativity to study medication.

- If only Day is missing, impute the day 1
- If Day and Month are missing, impute the Month as January and the Day as 1.
- If the year of primary diagnosis is missing or the date of primary diagnosis is completely missing, then no date will be imputed.

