6.4.2 Secondary Efficacy Variables

The best overall response is defined as the best visit response recorded from the start of the treatment until disease progression/recurrence. This data will be summarized using frequency and percentage for

CONFIDENTIAL Document Date: 12MAY2023. ST-AD-032 version 01

Complete Response (CR), Partial Response (PR), Stable Disease (SD), and Progressive Disease (PD) for each treatment group.

- Overall Response Rate (ORR): The percentages of CR+PR will be calculated and presented along with 95% confidence intervals of these percentages.
- Clinical Benefit Rate (CBR): The percentages of CR+PR+SD>=24 weeks will be calculated and presented along with 95% confidence intervals of these percentages.
- Progression Free Survival (PFS): It is defined as time from the first dose of study drug to documented disease progression or death due to any cause. This variable will be analyzed via Kaplan-Meier methodology.

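### SAP 7.3 dates partial progression and death records by the adverse-event and medication rules; the start branch can put an event before a progression-free scan, and the SAP does not say which branch applies

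*SAP*

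**What the plan says.** SAP 7.3 gives efficacy dates two sentences. Wholly missing dates are left alone: "For time-to-event endpoint if the date is completely missing, no imputation will be performed". Partial dates are sent elsewhere: "the incomplete/partial dates will be handled following the general conventions as detailed for adverse events and concomitant medications".

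The conventions referred to stand earlier in SAP 7.3 and come in two branches.

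- **Start, only the day missing.** In the month of first dose, if the end date is not before first dose or is wholly missing, "then impute the start day as the day of first dose date". In any other month the day becomes the 1st.
- **Start, day and month missing, year of first dose.** For an adverse event, under the same condition, "impute the start Month and Day as the Month and Day of first dose date". For the other type of record, "For medication, impute the start Month as January and the Day as 1". In any other year both become 1 January.
- **End, only the day missing.** "The last date of the month and year reported or the date of the final contact with the patient", taking the earlier of the two.
- **End, day and month missing.** 31 December of the recorded year or the last study contact, again the earlier.

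SAP 6.4.2 says of PFS: "It is defined as time from the first dose of study drug to documented disease progression or death due to any cause". DoR runs from first response, and duration of clinical benefit (DoCB) from first dose, to the same kinds of event. All three are censored at the last date the patient is known to be radiologically progression free (SAP 6.4.3 and 8.7.2).

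**The concern.** A progression or death date is neither the start nor the end of an adverse event or a medication course, and the SAP does not say which of these it should be treated as. Two programmers could both follow SAP 7.3 and report different PFS times for the same patient.

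The start branch also fits badly in itself. SAP 7.3 gives its purpose as working out durations or timing relative to study medication. Pulling an unknown onset to the first dose is a reasonable way to decide whether an adverse event began on treatment. It has no rationale for progression, because a patient with a later progression-free scan cannot have progressed on the day of first dose. The branch never looks at that scan, although the SAP uses the same information for censoring.

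At stake are the event times in the Kaplan-Meier analyses of PFS, DoR and DoCB, in a trial planned with 20 patients per group.

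**Working it through.** The plan gives no figure to reproduce. The check applies its rules to illustrative records. All calendar dates below are assumptions.

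**Inputs.** Start and end rules: SAP 7.3. Day count: imputed date − first dose date + 1, or without the + 1 if before first dose (SAP 6.2.1). Six-month cut-off: 180 days (SAP 6.4.1). C3D1 is Day 57 (SAP 6.2.2). A progression record has no end date of its own, so the condition in the start rule is met.

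**PFS with first dose on 15 March 2022**

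| Progression recorded as | Last contact | Start, adverse-event version | Start, medication version | End |
|---|---|---|---|---|
| 2022 | 10 Jan 2023 | 15 Mar: 0 + 1 = Day 1 | 1 Jan: 73 days before first dose | 31 Dec: 291 + 1 = Day 292 |
| 2022 | 20 Oct 2022 | Day 1 | 73 days before first dose | 20 Oct (cap): 219 + 1 = Day 220 |
| Sep 2022 | 20 Oct 2022 | 1 Sep: 170 + 1 = Day 171 | Day 171 | 30 Sep: 199 + 1 = Day 200 |
| Mar 2022 | 20 Oct 2022 | 15 Mar: Day 1 | Day 1 | 31 Mar: 16 + 1 = Day 17 |

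If the recorded year is later than the first-dose year, Day 1 does not arise. With first dose on 15 October 2022, progression recorded as 2023 and last contact on 10 January 2024, the start rule gives 1 January 2023 (78 + 1 = Day 79) and the end rule 31 December 2023 (442 + 1 = Day 443).

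**Gap with only the day missing.** At most 31 − 1 = 30 days. In the September example it is 200 − 171 = 29 days, and the two values lie on either side of Day 180.

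**Conflict with a scan.** C7D1 falls on Day 6 × 28 + 1 = 169, with a window of ±7 days, so Days 162 to 176. A progression-free scan on 5 September 2022 is Day 175, inside the window. If progression is then recorded as September 2022, the start rule gives 1 September (Day 171), four days before that scan.

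**Negative DoR.** Suppose partial response at C3D1, Day 57 = 10 May 2022, and progression recorded as 2022. The adverse-event start rule gives 15 March, 56 days before the response began.

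**End rule and scans.** It returns the earlier of period end and last contact. If the record is right, progression lies inside the recorded period and after the last progression-free scan, so period end cannot precede that scan. Nor can last contact precede a scan the patient attended.

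**End rule and death.** The cap has a different weakness. With last contact on 20 September and death recorded as October 2022, the earlier of 31 October and 20 September is 20 September. That lies outside the recorded month, on a day the patient was known to be alive.

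**The case against.** The strongest reply is that this will hardly ever matter. Progression comes from RECIST scans about every eight weeks, and the shell for Listing 16.2.6.4 holds the date of first radiological evidence as a full day, month and year. This stands: the documents do not say how many dates are partial, and few are likely to be. Some routes to a partial date remain: progression by tumour marker (protocol 8.5, SAP 8.7.2), efficacy information collected remotely at the end-of-study contact (protocol 1.6), and deaths more than 30 days after the last treatment (protocol 7.3.2).

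It can also be said that an event date is naturally an onset, so only the start branch applies. That would remove the ambiguity but leave the worse branch in force.

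A reader might infer three stronger things that the documents do not support.

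- **That the same patient would commonly get Day 1 or 31 December.** This needs day and month both missing, progression in the first-dose year, and contact up to year end. Patients are discontinued at confirmed progression (protocol 4.3) and followed for 30 days after the last dose (protocol 6.9), so the end rule will often return last contact instead.
- **That both branches can place progression before a progression-free scan.** Only the start branch can.
- **That one misdated event moves the 6-month rate by 1/20 = 5 points.** SAP 6.4.1 and 6.4.3 define the 6-month and 1-year rates by progression status. The shell footnotes for Tables 14.2.1.1 and 14.2.1.4 instead count patients with treatment duration of at least 180 or 360 days, which needs no progression date. The 5-point effect is therefore not established.

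**Conclusion.** Wrong as written. SAP 7.3 states a rule for partial efficacy dates, so this is not a gap. It leaves the branch open, and its start branch can give impossible or biased times: PFS of 1 day, an event 73 days before first dose, or a DoR of −56 days in the examples. With only the day missing the branches differ by up to 30 days, enough to cross Day 180.

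The clear exposure is Kaplan-Meier PFS, DoR and DoCB. The 6-month and 1-year rates are affected only if they are programmed from SAP 6.4 rather than from the shell footnotes. The examples rest on assumed dates, and the number of partial dates is unknown and probably small. The case for changing the sentence rests on the error being plain and the change cheap, not on a large expected effect.

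**What to change.** Before database lock, replace the cross-reference in SAP 7.3 with a rule for efficacy dates.

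1. Progression found on a scan takes the scan date.
2. A partial progression date becomes the later of the first day of the recorded period and the day after the last progression-free assessment. It is never before first dose and not after last contact.
3. A partial death date becomes the later of the first day of the recorded period and the day after the date last known alive. It has no last-contact cap, because the cap can place death on a day the patient was alive.
4. Any date whose bounds conflict with the recorded month or year is queried.
5. All imputed efficacy dates are listed.

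In the examples, progression recorded as 2022 with a last progression-free scan on 10 May becomes 11 May (57 + 1 = Day 58). Progression in September 2022 with a progression-free scan on 5 September becomes 6 September (Day 176). Taking the earliest admissible date is a convention, and the listing lets a reader judge whether it matters.

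The cost is SAP wording only: no new data, visits or patients.

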7.4 Interim Analyses and Data Monitoring

No interim analysis or data monitoring is planned for this study.

7.5 Multi-Centre Studies and Pooling of Centres

Data from all the centres will be pooled together for the analysis.

7.6 Multiple Comparisons/Multiplicity

Not applicable.

Document Date: 12MAY2023

Page 13 of 106 ST-AD-032 version 01

7.7 Use of an "Efficacy Subset" of Patients

Not applicable to this study.

7.8 Active-Control Studies Intended to Show Equivalence

Not applicable to this study.

7.9 Examination of Subgroups

The following sub-group analysis will be performed only for demographics, baseline characteristics and efficacy tables:

de novo metastasis, recurrent (locoregional/distal) metastasis and Overall. 1.

8. STATISTICAL ANALYSIS

8.1 Disposition of Patients

A tabular presentation of the patient disposition data will be provided by treatment group and overall. It will include the number of patients screened, enrolled, randomized, completed cycle 3, 6, 9,12 and 15, as well as the number of dropouts, with reasons for discontinuation, number in each population sets, number of patients with dose reductions or interruptions (if applicable), number patients with discontinuations due AEs etc. All patients data will be used for this report.

8.2 Protocol Deviations

A full list of protocol deviations for the study report will be compiled prior to database closure. All deviations will be reviewed by the Medical monitor prior to database closure. Each deviation will be categorized as major and minor and a decision will be taken by medical monitor whether to include the patient in a PP analysis population.

Protocol deviations will be presented as number and percentage of patients with minor and major deviations in the study for each treatment group and overall for all the patients in Safety analysis set. This data will also be listed as appropriate.

8.3 Analysis Populations

The following analysis populations are planned for this study:

8.3.1 Safety Population

The Safety Population will include all patients who receive at least 1 dose of the study medication. This population will be used for safety analysis.

8.3.2 Intent-to-Treat (ITT) Population

The ITT is the primary analysis population and will include data from patients who have received at least 1 dose of study medication. This population will be used for efficacy assessment. Per definition, the ITT and Safety population are similar in this study.

CONFIDENTIAL Page 14 of 106 Document Date: 12MAY2023 ST-AD-032 version 01

8.3.3 Protocol (PP) Population

The PP Population is a subset of the ITT population and will include patients without major protocol deviations. This population will also be used for efficacy assessment.

A deviation from the protocol is an unintended and/or unanticipated departure from the procedures and/or processes approved by the Sponsor and the IRB/IEC and agreed to by the Principal Investigator. Protocol deviations will be documented by the clinical monitor throughout the course of monitoring visits. Principal Investigator will be notified of deviations in writing by the monitor. The IRB/IEC should be notified of all protocol deviations according to IRB/IEC reporting requirements. Examples deviations included but not limited to:

- Failure to obtain informed consent (e.g., there is no documentation of informed consent) for a patient;
- Informed consent is obtained after initiation of study procedures;
- Enrolment of patient who has failed to meet the inclusion/exclusion criteria.

8.3.5 Pharmacokinetics (PK) population

Not Applicable.

8.4 Demographic and Other Baseline Characteristics

All demographic and baseline summaries will be based on all the patients in the Safety analysis Set.

Demographic and baseline characteristics data will be summarized using descriptive statistics (n, mean, Standard Deviation, median, minimum, maximum) for continuous variables, and using frequencies and percentages for categorical variables by treatment groups and overall.

Demographic characteristics will include age, race, gender, height, etc.

Disease characteristics will include time from initial diagnosis to enrolment, staging, number of prior therapies, (systemic therapy, radiotherapy and cancer surgery), type of cancer (locally advanced/metastatic), type of metastasis (de novo/recurrent), time from date of last therapy to enrolment, ECOG performance status, etc.

The demographic and baseline characteristics will also be summarized by metastasis type (de novo metastasis, recurrent (loco regional/distal) metastasis) and overall.

8.5 Prior and Concomitant Therapy

Prior medications are those that are taken only prior to initial dose of study drug. Concomitant medications are those that were taken while on study drug. Also, the medications / non-drug treatments which start after study treatment end date will be termed as 'Concomitant'.

The medication data will be coded using WHO-Drug dictionary (WHODRUG GLOBAL B3 March 1, 2021) and the non-drug treatments data will be coded using MedDRA dictionary Version 24.0 (Hierarchy).

A summary of frequencies and percentages by ATC level 2 and Preferred Terms for each treatment group along with overall and the listing of the prior and concomitant treatments taken will be provided for all the patients in Safety Analysis Set.

CONFIDENTIAL Page 15 of 106

Document Date: 12MAY2023. ST-AD-032 version 01

8.6 Prior Therapies

Total number of prior systemic therapies in any setting and metastatic setting will be summarized using median and range. The prior systemic therapies in metastatic setting will include therapies give after the diagnosis of metastatic disease.

Number of prior systemictherapies in any setting and metastatic setting will be summarized using median and range. They will also be classified into-

- Chemotherapy
- Aromatase Inhibitors
- Fulvestrant
- CDK4/6 Inhibitors
- Others

The last prior therapy will be classified in the following categories and will be summarized by frequency and percentage-

- Chemotherapy
- **Aromatase Inhibitors**
- **Fulvestrant**
- CDK4/6 Inhibitors
- Tamoxifen

Document Date: 12MAY2023

8.7 Analysis of Efficacy Parameters

All efficacy parameters will be summarized using ITT and PP analysis set.

In situation, identical patients qualify in ITT and PP analysis set, the statistical summaries for such parameters will be presented only for ITT with corresponding note to avoid the replication of results.

8.7.1 Analysis of Primary Efficacy Variable

The primary endpoint will be analysed to assess the anti-tumour activity of tenalisib in patients with locally advanced or metastatic breast cancer.

The summary of patients without disease progression at the end of 6 months will be provided by frequency and percentage along with 95% confidence intervals of these percentages for both the treatment groups. The 95% confidence intervals of these percentages will be calculated using exact method based on binomial distribution.

The efficacy analysis will also be summarized by metastasis type (de novo metastasis, recurrent metastasis) and overall.

> Page 16 of 106 ST-AD-032 version 01

8.7.2 Analysis of Secondary Efficacy Variables

These secondary efficacy variables will be analysed and summarised to evaluate safety and tolerability of tenalisib.

• Overall Response Rate (ORR): It is defined as sum of CR and PR rates.

The percentages of CR+PR will be calculated and presented along with 95% confidence intervals of these percentages.

This data will be summarized using frequency, and percentage along with 95% confidence intervals of these percentages using exact method based on binomial distribution.

The corresponding listing will also be provided.

• Clinical Benefit Rate (CBR): It is defined as sum of CR, PR and SD at 24 weeks or longer.

The percentages of CR+PR+SD>=24 weeks will be calculated and presented along with 95% confidence intervals of these percentages.

This data will be summarized using frequency, and percentage along with 95% confidence intervals of these percentages using exact method based on binomial distribution.

The corresponding listing will also be provided.

Progression Free Survival (PFS): It is defined as time from the first dose of study drug to
documented disease progression or death due to any cause.
 PFS is measured from the time of first dose of study drug to radiographic (or tumour marker as
applicable) documentation of disease progression or death due to any cause. Patients who did not
progress or die will be censored on the last date the patient is known to be radiologically
progression free. The summary table for PFS rate at 6-Month and 1-year by metastasis type will
also be provided.

This variable will be analyzed via Kaplan-Meier methodology and displayed graphically for each treatment group and overall. The following reports will be generated:

- The Q1, median and Q3 PFS time will be provided. The 95% CI for the Q1, median, and Q3 PFS time will be presented for each treatment group and metastasis group using Brookmeyer-Crowley method.
- The number and % of patients with disease progressive events (further divided into progression or death) will be provided.
- The number and % of patients censored (further divided by reasons for censoring) will be provided.
- Kaplan-Meier curves will be produced.
- · A listing of PFS data will be provided.

Additional efficacy variables

Duration of Treatment: Duration of treatment is defined as the time from first dose to last dose of drug.

Duration of response: Duration of response (DoR) is defined as the time from the first occurrence of partial or complete response to disease progression or death in patients who achieve complete or partial response. For patients who neither progress nor die, the duration of response will be censored on the last date the patient is known to be radiologically progression free. This variable will be analyzed via Kaplan-Meier methodology for each treatment group and overall as well as metastasis type and overall.

• The number and % of patients with partial or complete response.

• The number and % of patients censored (further divided by reasons for censoring) will be provided.

CONFIDENTIAL Page 17 of 106
Document Date: 12MAY2023. ST-AD-032 version 01

• The Q1, median and Q3 will be provided. The 95% CI for the Q1, median, and Q3 will be presented using Brookmeyer-Crowley method.

Duration of Clinical benefit: Duration of clinical benefit (DoCB) is defined as the time from the first dose of the study drug to disease progression or death in patients who achieve complete response, partial response, or stable disease for 24 weeks or longer. For patients who neither progress nor die, the duration of response will be censored on the last date the patient is known to be radiologically progression free. This variable will be analyzed via Kaplan-Meier methodology for each treatment group and overall as well as metastasis type and overall.

- The number and % of patients with partial or complete response or stable disease with 24 weeks or longer.
- The number and % of patients censored (further divided by reasons for censoring) will be provided.
- The Q1, median and Q3 will be provided. The 95% CI for the Q1, median, and Q3 will be presented using Brookmeyer-Crowley method.

Figures will be provided for best tumor response of each patient in Waterfall plot and visit wise tumor response by plotting with change from baseline.

